5.5.7.5. Echocardiograms

The actual value and change from Baseline to each on-treatment time point will be summarized for each ECHO parameter. A table summarizing the frequency and percent of subjects meeting the predefined markedly abnormal criteria at each visit will be presented. The predefined markedly abnormal criteria are defined below in Table 6. ECHO parameters will be listed by subject in a data listing.

Table 6 Predefined Markedly Abnormal Echocardiography Values

Variable	Units	Markedly Abnormal Criteria
LVEF	%	<55%
Fractional Shortening	%	<44%

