7.3. Study Endpoints

7.3.1. Safety Endpoints

Incidence of:

- Adverse events
- Clinical laboratory abnormalities
- Abnormalities in vital signs and physical examinations
- Abnormalities on electrocardiograms (ECGs) and echocardiograms (ECHO)

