10.3.6. Echocardiogram

A standard 2-dimensional (2D) ECHO will be obtained at the time points specified in Section 2. ECHOs will be performed at a consistent time of day throughout the study. The ECHO will be reviewed and interpreted by medically qualified personnel using a central vendor according to pre-specified criteria. Ejection fraction (EF) will be noted. The Investigator will review the results of the ECHO report and determine if the findings are clinically significant.

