13.8.2.5. Echocardiograms

The actual value and change from Baseline to each visit will be summarized by treatment condition for each ECHO for EF.

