5.5.6 Efficacy

5.5.7 Safety

Safety analyses will be descriptive in nature.

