5.5.7.1.1. Adverse Events of Special Interest

Summaries of TEAEs of special interest (AESIs) and other AEs of Interest will be summarized by SOC and PT. All SMQs listed below will include broad and narrow terms. The AESIs are:

- Hypersensitivity (Anaphylactic Reaction SMQ and Anaphylactic/Anaphylactoid Shock Conditions SMQ)
- Renal Toxicity (Acute Renal Failure SMQ)
- Leukopenia and Neutropenia (Haematopoietic SMQ)
- Infusion Site Reactions (Extravasation Events SMQ and the following PTs: Application Site Erythema, Application Site Rash, Catheter Site Haematoma, Catheter Site Haemorrhage, Catheter Site Related Reaction, Infusion Site Rash, Infusion Site Swelling)
- Severe Cutaneous Adverse Reactions (Severe Cutaneous Adverse Reactions SMQ)
- Infusion Related Reactions (PTs of Nausea, Vomiting, Pyrexia, Body
 Temperature Increased, Erythema, Flushing Infusion Related Reaction,
 Hypotension, Blood Pressure Decreased, Diastolic Hypotension, Orthostatic
 Hypotension, Procedural Hypotension, Blood Pressure Ambulatory Decreased,
 Blood Pressure Diastolic Decreased, Blood Pressure Orthostatic Decreased, Blood
 Pressure Systolic Decreased, Blood Pressure Systolic Inspiratory Decreased)
- Drug Induced Hepatotoxicities (Cholestasis and Jaundice of Hepatic Origin SMQ, Hepatic Failure, Fibrosis and Cirrhosis and Other Liver Damage-Related Conditions SMQ, Hepatitis, Non-infectious SMQ, Liver Neoplasms, Benign (incl Cysts and Polyps) SMQ, Liver Malignant Tumours SMQ, Liver Tumours of Unspecified Malignancy SMQ, Liver Related Investigations, Signs and Symptoms SMQ, Liver-Related Coagulation and Bleeding Disturbances SMQ)
- Cardiac Events (Cardiomyopathy SMQ, Cardiac Failure SMQ, and Arrhythmia Related Investigations, Signs and Symptoms SMQ)
- Coagulopathy (Haemorrhage Terms (excluding lab terms) SMQ, Haemotopoietic Thrombocytopenia SMQ, PTs in the Embolism and Thrombosis High Level Group Terms (HLGT)

The Other AEs of Interest are:

 Port-Related Events⁺ (Embolic and Thrombotic Events, Venous SMQ, Extravasation Events (Injections, Infusions and Implants) SMQ, PTs in the following High Level Terms (HLTs): Sepsis, Viraemia and Fungaemia NEC, Implant and Catheter Site Reactions, PTs in the following HLGTs: Endocardial Disorders and Device Issues. In addition, a search will be performed on the verbatim terms for "port", "central venous" and "central line")

- Fractures (PTs in the following HLGTs: Fractures and Bone and Joint Injuries)

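### SAP Table 6 sets LVEF <55% beside an unsourced fractional shortening limit of <44%; under simple geometry the two describe different levels of function, so the rows would usually disagree

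*SAP*

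**What the plan says.** Protocol section 7.3.1 makes the incidence of "Abnormalities on electrocardiograms (ECGs) and echocardiograms (ECHO") a safety endpoint. For echocardiograms the protocol names one parameter: section 10.3.6 has EF noted from a centrally read scan, and section 13.8.2.5 states "The actual value and change from Baseline to each visit will be summarized by treatment condition for each ECHO for EF".

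SAP section 5.5.7.5 goes further. It summarises every echocardiogram parameter and adds a count: "A table summarizing the frequency and percent of subjects meeting the predefined markedly abnormal criteria at each visit will be presented". The criteria are the two rows of Table 6: LVEF below 55%, and "Fractional Shortening % <44". No source, age range or baseline condition accompanies either limit. SAP section 6 declares only the Holter change, and SAP section 7 lists no references. The central vendor's reading criteria, mentioned in protocol section 10.3.6, are not reproduced in either document.

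**The concern.** LVEF and FS both measure how far the left ventricle contracts, so two limits that share one label in one table would be expected to mark roughly similar function. They do not appear to: 44% looks high for FS beside 55% for LVEF.

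This count is the only echocardiogram frequency table in the SAP. Laboratory tests (section 5.5.7.2) and ECGs (section 5.5.7.4) also have shift tables; echocardiograms do not. The study has one arm, so no control group would show that a high FS count came from the limit and not from the patients. A reader could see two quite different rates of marked cardiac abnormality at the same visit and have no way to choose between them.

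**Working it through.** **Inputs from the documents.** LVEF limit 55% and FS limit 44% (SAP Table 6); about 20 patients (SAP section 5.1). The SAP gives no derivation of 44%, so there is no planned calculation to reproduce.

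**Assumption, not from the documents.** FS is the proportional fall in ventricular diameter. For a uniformly contracting ellipsoid whose two short axes shorten by FS and whose long axis shortens by L,

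EF = 1 − (1 − FS)² × (1 − L).

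The bracket runs from L = 0 (short axes only) to L = FS (equal shortening on all axes).

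**What FS 44% means as EF**
- L = 0: 1 − 0.56² = 68.6%
- L = 5%: 1 − 0.56² × 0.95 = 70.2%
- L = 20%: 1 − 0.56² × 0.80 = 74.9%
- L = FS: 1 − 0.56³ = 82.4%

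**What LVEF 55% means as FS**
- L = 0: 1 − 0.45^(1/2) = 32.9%
- L = FS: 1 − 0.45^(1/3) = 23.4%

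The FS limit is therefore 44 − 32.9 = 11.1 to 44 − 23.4 = 20.6 percentage points above the FS that matches the LVEF limit. No value of L in the bracket yields 44% from 55%.

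**Discordant band.** At FS 33% the formula gives EF of 1 − 0.67² = 55.1% to 1 − 0.67³ = 69.9%, which is not below 55% at either end. So from FS of about 33% to just under 44%, a patient meets the FS limit and not the LVEF limit across the whole bracket. With equal shortening on all axes the band starts at about 23%.

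**One example.** EF 65% is ten points above the LVEF limit. It corresponds to FS of 1 − 0.35^(1/2) = 40.8% or 1 − 0.35^(1/3) = 29.5%. Both are below 44%.

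**Hypothetical counts.** The documents contain no EF or FS data. The normal EF distributions below are invented, to show only how far the answer moves with the assumption. Count = 20 × Φ((cut − mean)/SD), with cuts of 55 (LVEF), 68.64 (FS, L = 0) and 82.44 (FS, L = FS).

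| Assumed EF (mean, SD) | LVEF row | FS row, L = 0 | FS row, L = FS |
|---|---|---|---|
| 70, 6 | 0.1 | 8.2 | 19.6 |
| 65, 8 | 2.1 | 13.5 | 19.7 |
| 60, 8 | 5.3 | 17.2 | 19.9 |

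The FS row exceeds the LVEF row in every case. The size of the excess is set by the assumptions.

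**The case against.** The SAP never says that the two rows are equivalent or should flag the same patients. The conflict appears only once a geometric model is brought in from outside, and in a given patient regional wall motion or the method of measuring EF can separate the two values. This stands, and is why the finding says usually. It does not account for a gap of 11 to 21 FS points that runs in one direction across the bracket.

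Sensitive or uneven limits occur elsewhere in the SAP. Hemoglobin is markedly abnormal at anything below the lower limit of normal (Table 3-1), and AST and ALT use different multiples of baseline (Table 3-2). So one row flagging more than its neighbour is not in itself an error. That is fair, but the low-hemoglobin rule at least states its reference point, whereas the 44% is a bare figure.

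The LVEF limit is equally unsourced, and the vendor's criteria, which cannot be seen, might explain 44%. This also stands. A reader might infer that 44% is a typing error or that the FS row is the wrong one. The documents do not show that; they show only that the two limits have not been reconciled.

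Finally, the table is descriptive: "Safety analyses will be descriptive in nature". The protocol's named echocardiogram analysis is EF alone, so FS is an addition to it. This keeps the point minor.

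**Conclusion.** The point holds as a minor inconsistency. Table 6 gives one label to two limits that, under simple geometry, lie far apart: FS 44% corresponds to EF of about 69% to 82%, against an LVEF limit of 55%. Patients with FS between about 33% and 44% would usually be counted on FS alone. This rests on the assumption of uniform contraction, with long-axis shortening between zero and FS.

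Two further inferences are not supported. The first is any particular number of affected patients: at an assumed EF of mean 70 and SD 6, the FS count runs from 8.2 to 19.6 of 20 depending only on the conversion. The second is that the FS row would be nearly full from the start and so could not register decline. With L = 0 and an assumed mean EF of 65 (SD 8), a 10-point fall in the mean takes the FS row from 13.5 to 19.1 of 20. At mean 70 (SD 6) it goes from 8.2 to 18.5, while the LVEF row goes from 0.1 to 4.0. No claim about insensitivity is made.

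The consequence is confined to a possibly misleading FS frequency in one by-visit table. The LVEF row, actual values, changes from Baseline and listings are unaffected. So are the site review in protocol section 10.3.6 ("The Investigator will review the results of the ECHO report and determine if the findings are clinically significant") and the adverse-event summary in SAP section 5.5.7.1.1 that begins "Cardiac Events (Cardiomyopathy SMQ, Cardiac Failure SMQ".

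**What to change.** Before database lock, check both Table 6 limits against their source, for example the central echocardiogram vendor's reference ranges. Reconcile them so that the two rows describe comparable levels of function, correct whichever limit is out of line, and state the source in the SAP. If 44% proves deliberate, record its source and the reason it differs from the LVEF row. If the FS limit cannot be sourced, remove the FS row from the abnormality count and keep FS in the descriptive summaries and listings.

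The cost is an edit to one SAP table and a line giving the source. No new data are needed.

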5.5.7.6. Holter Monitoring

Holter monitoring data will be provided in a data listing. A separate listing will be created for hourly values and summary values.

5.5.7.7. Physical Examinations

Physical examination results will be listed by subject in a data listing.

6. CHANGES FROM PLANNED ANALYSES

This SAP has made the following change to the planned analyses in the protocol (Amendment 1, 05 July 2016):

• Holter monitoring was to be summarized. It will instead be listed only.

